4.1 Inclusion criteria

Subjects eligible for inclusion in this study have to fulfill all of the following criteria:

1. Able and willing to provide written informed consent and in the opinion of the Investigator, the subject is able to complete the duration of the study
Note: Informed consent must be obtained before any assessment is performed.
2. Male or female GA subjects ≥ 50 years of age
3. GA in BOTH EYES. **One eye MUST meet the following criteria** with lesion size assessed by FAF and measured by the CRC.
 - IF GA lesion is multifocal, THEN the total lesion area must be between 3-16 mm² and at least one lesion with an area of at least 1.25 mm²
 - IF GA lesion is unifocal, THEN the lesion area must be between 8-16 mm²
4. Presence of hyper-autofluorescence adjacent to at least 10% of the perimeter of GA the study eye

4.2 Exclusion criteria

Subjects fulfilling any of the following criteria are not eligible for inclusion in this study. No additional exclusions may be applied by the Investigator, in order to ensure that the study population will be representative of all eligible subjects.

1. Pregnant or lactating women and women of child-bearing potential (defined as all women physiologically capable of becoming pregnant). Women are considered post-menopausal and not of child bearing potential if they have had:
 - 12 months of natural (spontaneous) amenorrhea with an appropriate clinical profile (e.g. age appropriate, history of vasomotor symptoms)
 - Total hysterectomy
 - Surgical bilateral oophorectomy (with or without hysterectomy)
 - Tubal ligation for at least six weeks
 - Oophorectomy alone is acceptable ONLY when the reproductive status of the woman is confirmed by follow up hormone level assessments and she is considered to be not of child bearing potential
2. Subjects demonstrating any medical condition (systemic or ophthalmic) that may, in the opinion of the Investigator, and based on the content of the IB, preclude the safe administration of test article or safe participation in this study
3. Any contraindications or hypersensitivities to any component of the LFG316 or CLG561 solution
4. Any contraindications to IVT injections
5. Retinal disease, other than AMD, in either eye

Note: Benign conditions of the vitreous or peripheral retina are NOT excluded. Significant peripapillary atrophy either present at the time of Screening or which is expected to merge with the GA lesion during the course of the study, IS excluded.
6. Any history of, or current evidence of, CNV in either eye, as determined by FA at screening
7. Media opacity that interferes with fundus imaging in either eye, or is likely to require surgery during the study period
8. Any active ocular or periocular infection or active intraocular inflammation in either eye at screening or at baseline (e.g., infectious blepharitis, infectious conjunctivitis, keratitis, scleritis, endophthalmitis)
9. Any history of the following in either eye at screening:
 - herpes simplex keratitis
 - herpes zoster keratitis
 - infectious uveitis
10. Penetrating ocular surgery requiring cutting of ocular tissue (e.g., cataract surgery, PRK, LASIK, Epilasik, pterygium removal, etc.) or ocular trauma requiring medical or pharmacological treatment in the study eye within 90 days of screening

Note: Ocular laser procedures are not excluded
11. Macular atrophy in either eye due to anything other than AMD

Novartis

Confidential

Page 53

Amended Protocol Version No. 01 (Clean)

Protocol No. CCLG561X2201A

12. Concomitant treatment for AMD in either eye within 90 days of screening
Note: Concomitant use of vitamins/supplements is not excluded
13. Any periocular or IVT injections in either eye within 90 days of baseline
14. Any of the following abnormal vital signs at screening: temperature > 100.5° F (38° C); heart rate > 100 bpm; systolic blood pressure < 90 mmHg or > 160 mmHg, diastolic blood pressure > 95 mmHg.
Note: Out of range vital signs may be repeated once. If the values are still out of range the visit must be rescheduled. If out of range vitals are observed again and persistent at re-measurement, the subject must be disqualified from the study. Subjects may be rescreened when values have stabilized.
15. Uncontrolled ocular hypertension or glaucoma in the study eye (IOP > 25 mmHg despite current pharmacological or non-pharmacological treatment)
16. Participation in any interventional clinical trial within 12 weeks prior to screening
17. Any history of participation in interventional clinical trials involving gene therapy or extended release products, or any product with expected long term efficacy

5 Restrictions for study subjects

During recruitment, screening/informed consent review, and baseline visit, the subjects must be informed and reminded of the following restrictions:

In general, systemic medications are allowed; however, corticosteroids (ophthalmic or systemic) should only be used if necessary.

- For both eyes, topical ophthalmic corticosteroids are allowed, however, for the study eye, no IVT ophthalmic agents are allowed
- For the fellow eye, there is no restriction to the use of any topical or IVT ophthalmic agents, provided they are not investigational products

5.1 Contraception requirements

Please refer to the exclusion criteria ([Section 4](#)) for details of contraception requirements for the study.

5.2 Prohibited treatment

ELECTIVE intraocular surgeries are prohibited in both eyes.

Any IVT treatments, other than the study treatment, to the study eye are prohibited. If needed, the study ophthalmologist should administer the required IVT treatment (e.g. Lucentis for new onset choroidal neovascularization) to the study eye promptly. However, the study subject who receives the intervention MUST be discontinued from the study and undergo the follow up visit and end of study evaluation.

Novartis

Confidential

Page 54

Amended Protocol Version No. 01 (Clean)

Protocol No. CCLG561X2201A

6 Treatment

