3.1 Study design

This study employs a multi-center, randomized, sham-controlled, single-masked design. Approximately 114 eligible subjects (38 in each treatment arm) with GA will be randomized in a 1:1:1 ratio to obtain approximately 90 evaluable subjects completing the study per protocol. Subjects will receive one of three treatment modalities:

1. CLG561 (10 mg/100 µL)
2. CLG561 (5 mg/50 µL) + LFG316 (5 mg/50 µL)
3. Sham injection

The treatment modalities will occur every 28 days for a total of 12 injections (or sham injections). Subjects assigned to receive sham injections will be treated in the same manner as those assigned to the other two treatment arms, except that the hub of an empty syringe (without a needle) is placed against the eye. For the subjects receiving the CLG561 + LFG316 combination, the drugs are mixed extemporaneously and then injected in a single administration.

[figure not shown]
Both eyes must have GA. Only one eye MUST meet the other inclusion/exclusion criteria to be eligible for study participation. Randomization is 1:1:1 (CLG561: CLG561 + LFG316: Sham Injection) and assigned by the IRT.

The study consists of up to 30-Day screening period, an approximate 336-Day treatment period (12 IVT injections occurring approximately every 28 days), and a follow up period consisting of two follow up visits occurring 4 and 16 weeks after the last administered injection.

If a subject prematurely exits the study, then he/she must return to the clinical site approximately 4 weeks after their last injection (or the earliest possible date after 4 weeks) for the EOS evaluation. In this case, all assessments must be completed at the EOS visit.

The following will be masked to treatment assignment:

- Subjects
- Visual acuity assessor at the study site
- Technicians obtaining images at the study site

Figure 3-1 Study design

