6.9 Rescue medication

Use of rescue medication is not allowed. Any IVT treatments, other than the study treatment, to the study eye are prohibited. If needed, the study ophthalmologist should administer the required IVT treatment to the study eye promptly. However, the study subject who receives the intervention will be discontinued from the study and undergo the follow up visit and end of study evaluation. The required IVT treatment must be recorded on the Concomitant medications/Significant non-drug therapies eCRF after start of study drug.

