7.1 Discontinuation of study treatment

Subjects may voluntarily discontinue study treatment for any reason at any time.

The Investigator must discontinue study treatment for a given subject if he/she believes that continuation would be detrimental to the subject's well-being.

Study treatment **must** be discontinued under the following circumstances:

- Subject withdraws consent
- Pregnancy
- Any condition in the study eye requiring additional IVT treatment
- Any condition requiring intraocular surgery in the study eye
- Use of any ocular (in either eye) or systemic investigational treatments
- Use of prohibited treatment as per [Section 5.2](#)
- Any other protocol deviation that results in a significant risk to the subject's safety

Subjects who discontinue study treatment or who decide they do not wish to participate in the study further should NOT be considered withdrawn from the study UNLESS they withdraw their consent (see [Section 7.3](#)). If they fail to return for these assessments for unknown reasons, every effort (e.g. telephone, e-mail, and letter) must be made to contact them as specified in [Section 7.2.1](#).

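### After non-study intravitreal treatment in the study eye, Sections 5.2 and 6.9 discontinue the subject from the study, while Section 7.1 stops study treatment and does not count the subject as withdrawn

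*Protocol*

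**What the plan says.** Section 5.2 bars intravitreal (IVT) treatment of the study eye other than study treatment, but tells the ophthalmologist to give it promptly if needed. Its example is Lucentis for new choroidal neovascularization (CNV). It then states that "the study subject who receives the intervention MUST be discontinued from the study", after a follow-up visit and an end-of-study (EOS) evaluation. Section 6.9 says the same: "the study subject who receives the intervention will be discontinued from the study".

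Section 7.1 lists circumstances in which *study treatment* must stop. One is "Any condition in the study eye requiring additional IVT treatment"; another is use of prohibited treatment, with a reference to Section 5.2. It closes by saying that subjects who discontinue study treatment "should NOT be considered withdrawn from the study UNLESS they withdraw their consent". On attendance it says: "If they fail to return for these assessments for unknown reasons, every effort" must be made to contact them.

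Section 3.1 brings back a subject who exits prematurely "approximately 4 weeks after their last injection (or the earliest possible date after 4 weeks) for the EOS evaluation", and adds: "In this case, all assessments must be completed at the EOS visit". The same section describes the regular follow-up period as "two follow up visits occurring 4 and 16 weeks after the last administered injection".

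**The concern.** One event leads to two different study statuses. Under 5.2 and 6.9 the subject leaves the study. Under 7.1 the subject stops dosing, is not withdrawn, and is pursued if assessments are missed. Section 7.1 cites 5.2 by number, so it is not a general rule that simply yields to a more specific one.

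The choice decides whether later data exist. Safety is the first primary objective, with changes assessed through Day 421 (Section 2.1), and the combination has not been given to humans before (Section 3.6). CNV is excluded at entry, so in the protocol's own example the subject has a new ocular event on study. If that subject leaves, scheduled observation stops early. The full-analysis-set sensitivity analysis (Section 11.4.4) and the secondary FAF and acuity endpoints (Section 11.5.1) also lose assessments. An analysis plan cannot restore visits that were never held.

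**Working it through.** The protocol states no figure on this point, so the check compares texts and then works out visit dates.

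**Texts side by side**

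- Event: IVT treatment of the study eye other than study treatment (5.2, 6.9; two entries in the 7.1 list).
- Status under 5.2 and 6.9: discontinued from the study.
- Status under 7.1: study treatment stopped; not withdrawn unless consent is withdrawn.
- Last visit under 5.2 and 6.9: a follow-up visit and an EOS evaluation, with no timing. Section 3.1 offers about 4 weeks after the last injection (early exit), or 4 and 16 weeks (regular follow-up).

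**Inputs for the dates**

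- Injections every 28 days, from Day 1 to Day 309 (Table 8-1).
- FAF endpoint days 85, 169, 253, 337 and 421 (Sections 2.1, 2.2, 11.5.1).
- Windows of ±5 days at these visits and ±7 days at Day 421 (Table 8-2).
- *k* = day of last study injection. The 4-week reading ends at *k* + 28. The 16-week reading has visits at *k* + 28 and *k* + 112.

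An endpoint FAF counts as missed if no attended visit falls in its window. Days short = 421 minus the last visit.

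| *k* | Last visit, 4-week | FAF days missed | Days short | Last visit, 16-week | FAF days missed | Days short |
|---|---|---|---|---|---|---|
| 85 | 113 | 169, 253, 337, 421 | 308 | 197 | same | 224 |
| 169 | 197 | 253, 337, 421 | 224 | 281 | same | 140 |
| 253 | 281 | 337, 421 | 140 | 365 | same | 56 |
| 281 | 309 | 337, 421 | 112 | 393 | same | 28 |
| 309 | 337 | 421 | 84 | 421 | none | 0 |

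On the 16-week reading, Day 365 is 28 days after Day 337 and Day 393 is 28 days before Day 421. Both are outside the windows.

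**Per-protocol (PP) primary analysis.** Doses missed after *k* are (309 − *k*)/28, which gives 8, 5, 2, 1 and 0 for the five rows. Section 11.1 allows at most one missed dose in six months and no two in a row. A last injection on Day 253 or earlier fails both limits, so those subjects leave the PP set under either instruction. With *k* = 309 the Day 337 image is taken. Only *k* = 281 could touch the primary analysis: one dose missed, Day 253 available, Day 337 imputed.

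**What is kept.** All assessments are done at EOS, so an exit FAF exists, and it can count toward full-analysis-set membership (Section 11.1). Adverse events are followed until they resolve or are judged permanent (Section 9.3). A completer has 421 − 309 = 112 days after the last dose. The 16-week reading gives the same post-dose period, so what it loses is later off-treatment observation.

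**The case against.** The strongest reply is that the sections can be reconciled. Section 7.1 ties withdrawal to consent and does not expressly order the full visit schedule. Sections 5.2 and 6.9 do not stop all assessments, as Section 7.3 does on withdrawal of consent; they ask for a follow-up visit and EOS. The synopsis diagram places follow-up and EOS over Days 337 to 421. A site could stop dosing, hold those two visits, and pursue the subject if they are missed. That would keep the last two FAF days. This reading is possible, but it does not remove the conflict: the wording is discontinuation from the study, and Section 3.1 gives a premature exit one EOS visit at about 4 weeks. Sites should not have to choose.

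It can also be said that ending participation after new CNV and other IVT therapy is defensible in a proof-of-concept study with a PP primary set, since later study-eye data mix study drug, new disease and the other treatment. The interpretive point stands, and such data need a flag. It does not justify two statuses for one event, and observation through Day 421 is part of a primary endpoint.

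A reader might infer that nearly every remaining visit is lost, for example 9 of the 10 scheduled after Day 85. The documents do not support that count as a loss caused by 5.2 and 6.9. It includes monthly injection visits that 7.1 does not clearly require of a subject off treatment. The firmer measure is the FAF days and the safety observation to Day 421.

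**Conclusion.** The contradiction is in the text and should be corrected. On the 4-week reading, between one and four endpoint FAF assessments are lost in the cases tabulated, and scheduled observation ends 84 to 308 days before Day 421. On the 16-week reading the range is none to four assessments and 0 to 224 days. The loss falls on safety follow-up, the full-analysis-set sensitivity analysis and the secondary endpoints.

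A reader might infer that the primary efficacy result is at risk. The documents do not support this. Most affected subjects already fail the PP dosing rule. Even the Day 281 case may drop out of the PP set, because a critical protocol deviation also excludes a subject and the other IVT treatment could be classed as one. Nor do the documents support a claim that safety data disappear, given the exit evaluation and continued adverse-event follow-up.

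The dates assume nominal visit days and that the last injection means the last study injection. The protocol gives no rate of such events, so the number of subjects affected is unknown.

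**What to change.** In Sections 5.2 and 6.9, replace the discontinuation from the study, together with the clause on the closing visits, by: *discontinued from study treatment and, unless consent is withdrawn, continue the remaining scheduled FAF, acuity and safety assessments, including the Day 337 and Day 421 visits*. Replacing the closing-visit clause matters, because it is the source of the 4- versus 16-week ambiguity. In Section 3.1, state that the early-exit EOS visit applies only to subjects who leave the study. Flag study-eye data collected after the other IVT treatment. Prompt treatment, stopping study drug and Section 7.3 stay as they are. Attendance at injection-only monthly visits need not be required.

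The cost is amended wording in three sections and no new procedure. Each affected subject attends a few visits already on the schedule. Counting FAF days, these are 4, 3, 2 and 2 for last injections on Days 85, 169, 253 and 281, and at most 1 for Day 309. The downside is that images taken after the other IVT treatment need separate interpretation.

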6.1 Study treatment

Details on the storage and management of investigational product, randomization and instructions for preparing and administering study treatment are outlined in the MOP.

6.1.1 Investigational treatment

The investigational products CLG561 and LFG316 will be provided by the Sponsor and supplied to the Investigator. The Investigator will be responsible for the preparation of CLG561 injection and the co-administered dose of CLG561 and LFG316 injection.

Corporate Confidential Information

Subjects assigned to sham injections are treated in the same manner as those assigned to the other two treatment arms, except instead of an IVT injection, the hub of an empty syringe (without a needle) is placed against the eye.

6.2 Treatment arms

Subjects are assigned to one of the following 3 treatment arms in a ratio of 1:1:1.

1. IVT CLG561 (10 mg/100 μ L), administered every 28 days for total of 12 injections
2. IVT CLG561 5 mg + LFG316 5 mg co-injected in 100 μ L total volume via a single injection, administered every 28 days for total of 12 injections
3. Sham injections, administered every 28 days for total of 12 sham injections

6.3 Permitted dose adjustments and interruptions of study treatment

Study drug dose adjustments and/or interruptions are not permitted.

6.4 Treatment assignment

Subject numbers are assigned by the EDC in ascending, sequential order to all subjects who sign informed consent at each clinical site. The Investigator will enter the subject number in the IRT and EDC as required.

A randomization scheme is used to ensure that treatment assignment is unbiased and concealed from subjects and masked site staff. A randomization list is produced by or under the responsibility of the Sponsor using a validated system that automates the random assignment of treatment arms to randomization numbers in the specified ratio. The randomization scheme for subjects will be reviewed and approved by a member of the Sponsor randomization group.

6.5 Treatment masking

This is a single masked study. Subjects, the CRC, and select investigational staff (technicians performing visual acuity and obtaining images) are masked to the identity of study treatments.

6.6 Emergency breaking of assigned treatment code

The Investigator will have access to the assigned treatment code throughout the study because the study design is single masked. No emergency breaking of assigned treatment code is necessary based on the single masked design.

6.7 Treatment exposure and compliance

Pharmacokinetic parameters (measures of treatment exposure) are determined in all subjects treated with CLG561 or the combination of CLG561 and LFG316, as detailed in [Section 8.5](#).

6.8 Recommended treatment of adverse events

Medication used to treat AEs must be recorded on the Concomitant medications/Significant non-drug therapies eCRF.

6.9 Rescue medication

Use of rescue medication is not allowed. Any IVT treatments, other than the study treatment, to the study eye are prohibited. If needed, the study ophthalmologist should administer the required IVT treatment to the study eye promptly. However, the study subject who receives the intervention will be discontinued from the study and undergo the follow up visit and end of study evaluation. The required IVT treatment must be recorded on the Concomitant medications/Significant non-drug therapies eCRF after start of study drug.

6.10 Concomitant treatment

All prescription medications, over-the-counter drugs and significant non-drug therapies administered or taken within the timeframe defined in the entry criteria prior to the start of the study and during the study, must be recorded on the Concomitant medications/Significant non-drug therapies section of the eCRF.

Novartis

Confidential

Page 56

Amended Protocol Version No. 01 (Clean)

Protocol No. CCLG561X2201A

In general, systemic medications are allowed; however, corticosteroids (ophthalmic or systemic) should only be used if necessary.

- For both eyes, topical ophthalmic corticosteroids are allowed, however, for the study eye, no IVT ophthalmic agents are allowed.
- For the fellow eye, there is no restriction to the use of any topical or IVT ophthalmic agents, provided they are not investigational products

Medication entries must be specific to trade name, the single dose and unit, the frequency and route of administration, the start and discontinuation date and the reason for therapy.

7 Discontinuation and study completion

7.1 Discontinuation of study treatment

Subjects may voluntarily discontinue study treatment for any reason at any time.

The Investigator must discontinue study treatment for a given subject if he/she believes that continuation would be detrimental to the subject's well-being.

Study treatment **must** be discontinued under the following circumstances:

- Subject withdraws consent
- Pregnancy
- Any condition in the study eye requiring additional IVT treatment
- Any condition requiring intraocular surgery in the study eye
- Use of any ocular (in either eye) or systemic investigational treatments
- Use of prohibited treatment as per [Section 5.2](#)
- Any other protocol deviation that results in a significant risk to the subject's safety

Subjects who discontinue study treatment or who decide they do not wish to participate in the study further should NOT be considered withdrawn from the study UNLESS they withdraw their consent (see [Section 7.3](#)). If they fail to return for these assessments for unknown reasons, every effort (e.g. telephone, e-mail, and letter) must be made to contact them as specified in [Section 7.2.1](#).

